7.2.13 Concomitant Medications and Therapies

Collect all therapies and medications, prescription and over-the-counter, from the time of signed ICF through the 30-day Safety Follow-Up Visit, including any medication used to treat aEs or serious aEs (SAEs) during the 30-day follow-up period. In addition, at the 30-day Safety Follow-Up Visit, collect the time of initiation of new anticancer therapy. Use of concomitant medication should be documented. During the survival follow-up period, collect only anticancer therapies.

7.2.14 Adverse Event Assessment

Monitor patients for any untoward medical events (aEs or SAEs) from the time of signed ICF through 30 days after last dose of study medication. SAEs should be reported to Taiho Drug Safety or designee. If any medical occurrences outside the 30-day follow-up period are reported to or observed by the Investigator that he/she believes are related to the administration of the study medication, it is the Investigator's responsibility to record those events on the case report form. If any of those events are serious, then the investigator has to report this occurrence to Taiho Drug Safety or designee. See Section 8 for definitions and detailed reporting of aEs and SAEs.

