4 STUDY SCHEMA

Safety monitoring will begin at the time the Informed Consent Form (ICF) is signed and continue for 30 days after the last dose of study medication or until the initiation of another cancer therapy, whichever comes first.

At the end of treatment, all patients will be followed for survival at scheduled 8-week time intervals until 2 years.

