6.3 Study Medication Regimen, Administration, and Dose Reduction / Modification Procedures

6.3.1 Study Medication Regime

Each treatment cycle will be 28 days in duration. One treatment cycle consists of the following:

Days 1 through 5: TAS-102 (35 mg/m²/dose) orally 2 times daily with the first dose administered in the morning of Day 1 of each cycle and the last dose administered in the evening of Day 5.

Days 6 through 7: Recovery

Days 8 through 12: TAS-102 (35 mg/m²/dose) orally 2 times daily with the first dose administered in the morning of Day 8 of each cycle and the last dose administered in the evening of Day 12.

Days 13 through 28: Recovery

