6.3.5 Dose Hold and Resumption in Response to Hematologic Toxicities

Myelosuppression are described in the following table. Note that for all patients with decreases in neutrophils and/or platelets, the next cycle of study treatment should not be started until the resumption criteria are met even if the decreases do not meet the hold criteria.

Uncomplicated neutropenia or thrombocytopenia \leq Grade 3 does not require a reduction in dose of study medication. Patients who experience uncomplicated Grade 4 neutropenia or thrombocytopenia that results in a >1 week delay of the start of the next cycle should start the next cycle at one reduced dose level. If the delay is ≤ 1 week, the patient should start the next cycle at the same dose level.

Parameter	Hold Criteria		Resumption Criteria ^a
	Conventional Units	SI Units	
Neutrophils	$<500/\text{mm}^3$	$<0.5 \times 10^9/\text{L}$	$\geq 1500/\text{mm}^3$ (IU: $\geq 1.5 \times 10^9/\text{L}$)
Platelets	$<50,000/\text{mm}^3$	$<50 \times 10^9/\text{L}$	$\geq 75,000/\text{mm}^3$ (IU: $\geq 75 \times 10^9/\text{L}$)

^a These resumption criteria apply to the start of the next cycle for all patients regardless of whether or not the hold criteria were met.

Both conventional and SI (International System) units are presented in CTCAE v. 4.03.

Table 7. TAS-102 Dose hold and resumption criteria for hematologic toxicities related to myelosuppression

If the patient recovers from the toxicities to the resumption criteria defined above during the 2-week treatment period (treatment Days 1 through 5, 8 through 12), and no dose reduction is required, study

drug therapy may be resumed during that cycle. If a dose reduction is required, study drug therapy should be resumed at the start of the next cycle at the appropriate dose level. If the study drug dose is reduced, it must not be increased for subsequent cycles.

If the toxicities that are defined above recover during the recovery period (Days 13 through 28), start the next cycle on schedule at the appropriate dose level. If the toxicities that are defined above do not recover during the treatment or rest period, the start of the next cycle can be delayed for a maximum of 28 days from the scheduled start date of the next cycle. If resumption criteria are met by this maximum 28-day delay, start the next cycle at the appropriate dose level according to protocol.

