Patients who require more than a 28-day delay in the scheduled start date of the next cycle will have study medication discontinued.

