7.2.17 End of Treatment

The end of treatment is defined as the date when the Investigator determines that the patient will stop all study medication. If the decision to discontinue study medication is made within 2 weeks after the patient's last treatment visit, an End of Treatment Visit is not required unless deemed clinically necessary by the Investigator. If the decision to discontinue study medication (due to disease progression or other reasons) is made more than 2 weeks after the last treatment visit, an End of Treatment Visit is required. If this visit occurs within 2 weeks of the 30-day Safety Follow-up Visit, the 2 visits can be combined.

7.2.18 30-Day Safety Follow-up

A Safety Follow-up visit will be conducted 30 days after the last dose of study medication. If the patient starts new anticancer therapy within 30 days after the last dose of study medication, the 30-day Safety Follow-up Visit should be performed prior to the start of new anticancer therapy within the 30-day window. If this visit occurs within 2 weeks of the End of Treatment Visit, the 2 visits can be combined but should not take place less than 30 days after the last dose of study medication.

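### All-cause adverse-event collection can close 15 or more days before the latest end-of-treatment decision in patients who never restart after a toxicity delay

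*Protocol*

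**What the plan says.** The protocol ties safety collection to the last dose and the end of treatment to a decision.

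- **Collection window.** Section 7.2.14 monitors for AEs and SAEs "from the time of signed ICF through 30 days after last dose of study medication". Section 4 has safety monitoring "continue for 30 days after the last dose of study medication or until the initiation of another cancer therapy, whichever comes first".
- **Safety visit.** Section 7.2.18: "A Safety Follow-up visit will be conducted 30 days after the last dose of study medication".
- **Dosing calendar.** Section 6.3.1: "Each treatment cycle will be 28 days in duration", with "the last dose administered in the evening of Day 12".
- **Permitted wait.** Section 6.3.5: "the start of the next cycle can be delayed for a maximum of 28 days from the scheduled start date of the next cycle". It adds: "Patients who require more than a 28-day delay in the scheduled start date of the next cycle will have study medication discontinued". Section 7.4(a) lists the same limit among the criteria for removal.
- **End of treatment.** Section 7.2.17 defines it as "the date when the Investigator determines that the patient will stop all study medication".

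Four other provisions bear on the point. Section 7.2.14 still requires later events to be recorded if they come to the investigator's notice and are believed related, and reported if serious. Section 8.7 requires an AE that has occurred to be followed to the last study visit. Section 7.2.19 follows survival every 8 weeks. Appendix 1 draws the AE/SAE row as arrows through the End of Treatment, 30-day safety and survival follow-up columns.

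**The concern.** The two clocks can cross. While a patient waits for toxicity to resolve, nobody knows whether the dose already taken was the last. The 30-day count may run out during that wait, with the patient still formally on treatment. From then on, only events believed related, and brought to the investigator's notice, have to be recorded.

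The safety outcome in section 7.3.2 is the incidence, nature and severity of adverse events, with no limit to related events, and section 8.1 defines an AE regardless of cause. The uncovered time falls selectively on patients with the longest unresolved toxicity. In advanced pancreatic cancer a new infection or bleed can plausibly be put down to the disease, so the causality filter matters. With no control arm and 28 patients, a few missed events would show in the reported rates.

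**Working it through.** The protocol states neither Day 42 nor Day 57, so there is no printed figure to reproduce. Both follow from its rules.

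**Inputs**
- Cycle length 28 days, so the next cycle is due on Day 28 + 1 = Day 29 (section 6.3.1).
- Last planned dose in a cycle on Day 12 (section 6.3.1).
- Collection ends 30 days after the last dose (sections 4 and 7.2.14).
- Maximum delay 28 days past the due date (sections 6.3.5 and 7.4(a)).

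**Formulas**, with L the day of the last dose
- Collection closes on Day L + 30.
- Latest permitted start of the next cycle: Day 29 + 28 = Day 57.
- Delay already used when collection closes: (L + 30) − 29.
- Days uncovered up to Day 57: 57 − (L + 30).

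| Last dose | Collection closes | Delay at that point | Days uncovered to Day 57 |
|---|---|---|---|
| Day 12 (full cycle) | Day 42 | 13 days | 15 (Days 43–57) |
| Day 8 | Day 38 | 9 days | 19 |
| Day 5 (Days 8–12 held) | Day 35 | 6 days | 22 |
| Day 1 (extreme) | Day 31 | 2 days | 26 |

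After a full cycle the gap opens only when the delay exceeds 13 days. If dosing resumes, the last-dose date moves forward and the interval is covered.

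**Can the safety visit still be held?** Section 7.1 allows ±7 days for follow-up visits, and sections 7.2.17 and 7.2.18 let the safety and End of Treatment visits be combined if they fall within 2 weeks of each other. With the decision on Day 57:
- Last dose Day 12: latest safety visit Day 42 + 7 = Day 49. Then 57 − 49 = 8 days, so the visits can be combined. Counted from the nominal Day 42, the distance is 15 days and misses by one.
- Last dose Day 5: latest Day 35 + 7 = Day 42. Then 57 − 42 = 15 days, which misses by one.
- Last dose Day 1: latest Day 31 + 7 = Day 38. Then 57 − 38 = 19 days, which misses by five.

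**What falls through, by type of event**
- The toxicity that caused the delay began inside the window. It is recorded and followed (section 8.7).
- A new event after the window that is noticed and believed related is recorded, and reported if serious (section 7.2.14).
- A death is captured by survival follow-up (section 7.2.19).
- A new event after the window that is judged unrelated, or not noticed, is outside the collection rule.

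**Scale.** If all 28 patients form the safety denominator (an assumption), one patient with a missed event moves a rate by 1/28 = 3.6 percentage points and two by 2/28 = 7.1.

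**The case against.** The strongest reply is that a fixed window from the last dose, with an open-ended clause for related events, is a coherent choice, and that other sections already cover most of what might be lost. Much of this stands. Section 8.5 makes timing relative to the drug the decisive factor in attribution, and section 8.4 asks for the known association with the drug to be weighed. Infection or bleeding during unresolved myelosuppression is therefore among the events most likely to be called related and kept. The visit-combination rule resolves the safety-visit timing after a full cycle. The Day 1 case is extreme, since section 6.3.5 requires blood counts to meet the resumption criteria before a cycle starts.

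It can also be said that the Appendix 1 arrows already extend collection. They cannot settle the matter. The concomitant-medication arrows likewise run through survival follow-up, where section 7.2.13 limits collection to anticancer therapies. The arrows contradict the text rather than govern it. Section 8.7 does not close the gap either: it follows events that have occurred and sets no collection period for new ones.

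A reader might infer that the patients with the worst toxicity lose two weeks or more of safety data, or that their safety visit cannot be held on time. The documents do not support either statement in that form. The course of the delaying toxicity is kept, and after a full cycle the visit rules mostly cope.

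**Conclusion.** The point holds in a limited form. As written, routine all-cause collection can end 15 days before the latest end-of-treatment decision after a full cycle, 22 days if the last dose was on Day 5, and at most 26. This rests on a patient who uses the whole 28-day delay and never restarts; a shorter wait shrinks the gap or removes it. The possible loss is confined to new-onset events judged unrelated or not noticed. The protocol gives no basis for counting the patients affected, and the number is probably small. The loss is nonetheless selective, it sits badly with a safety outcome that counts events of any cause, and the conflict between Appendix 1 and sections 4 and 7.2.14 leaves sites without a clear rule.

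**What to change.** - **Sections 4, 7.2.14 and Appendix 1:** let AE/SAE collection run to the later of 30 days after the last dose and the End of Treatment visit, subject to the stop at new anticancer therapy already in section 4. Where section 7.2.17 does not require that visit, the decision date can take its place.
- **Section 7.2.18:** let the End of Treatment visit serve as the safety visit when discontinuation is decided more than 30 days after the last dose.
- **Section 7.2.13 and the Appendix 1 arrows:** align concomitant-medication collection and both arrow rows with the same end point.

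No dosing or delay rule changes. The cost is a wording amendment, a note on CRF completion, and a few more weeks of AE recording in a few patients. It should add little visit burden, because section 7.2.17 already requires an End of Treatment visit when the decision comes more than 2 weeks after the last treatment visit.

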7.2.15 Quality of Life Assessment

Quality of life will be assessed by validated EORTC QLQ-C30 questionnaire. As a self-administered survey, it incorporates 30 items comprising five functional scales (physical, role, cognitive, emotional,

and social), three symptom scales (fatigue, pain, and nausea and vomiting), as well as a global health and QoL scale. It will be completed by the patient at the time points listed below:

- Within 7 days prior to start of study treatment
- Prior to dose administration on Day 1 of Cycles ≥ 2
- At the 30-day safety follow-up (if not performed within the prior 4 weeks)

7.2.16 Exploratory Biomarker

Plasma / serum samples will be collected at baseline and before each cycle, and subsequently stored at -80°C for future proteomic profiling and exploratory biomarker evaluation. Upon buffer exchange, LysC/Trypsin enzymatic digestion and 11-plex TMT reagents' labelling, peptides will be fractionated using high pH reversed-phase liquid chromatography. Peptide identification and quantification will be performed using a Dionex Ultimate3000 nanoRSLC system coupled to a Thermo Fisher Orbitrap Fusion Lumos mass spectrometer.

7.2.17 End of Treatment

The end of treatment is defined as the date when the Investigator determines that the patient will stop all study medication. If the decision to discontinue study medication is made within 2 weeks after the patient's last treatment visit, an End of Treatment Visit is not required unless deemed clinically necessary by the Investigator. If the decision to discontinue study medication (due to disease progression or other reasons) is made more than 2 weeks after the last treatment visit, an End of Treatment Visit is required. If this visit occurs within 2 weeks of the 30-day Safety Follow-up Visit, the 2 visits can be combined.

7.2.18 30-Day Safety Follow-up

A Safety Follow-up visit will be conducted 30 days after the last dose of study medication. If the patient starts new anticancer therapy within 30 days after the last dose of study medication, the 30-day Safety Follow-up Visit should be performed prior to the start of new anticancer therapy within the 30-day window. If this visit occurs within 2 weeks of the End of Treatment Visit, the 2 visits can be combined but should not take place less than 30 days after the last dose of study medication.

7.2.19 Survival Follow-up after 30-Day Safety Visit

All patients will be followed for survival status (alive/dead) at scheduled 8-week ($+/ - 7$ days) time intervals until death. Patients will be followed until 12 months after the first dose of study medication for the last patient randomized, even if consent for study participation has been withdrawn. The Investigator should make every effort to contact the patient or primary caregiver to determine his/her survival status. Times and dates of contact must be documented in the patient's records.

7.2.20 By Visit Assessment

Detailed patient visit timetable is specified in Appendix 1.

7.3 Outcome Measures

7.3.1 Primary Outcome:

- **16-week progression-free survival (PFS) rate:** The percentage of study population alive and without progression (according to RECIST 1.1) at 16 weeks from the date of informed consent

7.3.2 Secondary Outcomes:

- **Progression-free Survival (PFS):** PFS is measured from the date of informed consent to radiographically documented progression according to RECIST 1.1 or death from any cause (whichever occurs first). Participants alive and without disease progression or lost to follow-up will be censored at the date of their last radiographic assessment
- **Time to progression (TTP):** TTP is measured from the date of informed consent to radiographically documented progression according to RECIST 1.1. Participants death and without disease progression, alive without disease progression, or lost to follow-up will be censored at the date of their last radiographic assessment
- **Overall survival (OS):** OS is measured from date of informed consent to the date of death from any cause. Participants alive or lost to follow-up will be censored at the date of their last radiographic assessment
- **Objective response rate (ORR):** The percentage of patients with radiologically complete or partial response as determined by the Investigator according to RECIST version 1.1.
- **Disease control rate (DCR):** The percentage of patients with radiologically complete response, partial response, or stable disease as determined by the Investigators according to RECIST version 1.1
- **Duration of response (DoR):** DoR is the time from documentation of tumor response to radiographically documented disease progression
- **Time to deterioration of ECOG performance status:** Time from date of informed consent until the first date on which ECOG performance status score of 2 or higher was recorded ⁽³⁶⁻³⁷⁾
- **Time to deterioration of quality of life:** Decrease from baseline of 10 points or more on the EORTC QLQ-C30 maintained for two consecutive assessments or a decrease of 10 points or more in one assessment followed by death from any cause within 3 weeks.
- **Safety outcome measures:** Incidence, nature, and severity of adverse events graded according to NCI-CTCAE v5.0

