7 FOLLOW UP AND OUTCOME EVALUATION

7.1 Follow-Up Schedule

The study assessments are described by procedure in the following sections. The study schedule must be followed with a window of +/- 3 days which is allowable for study procedures, as long as the proper order is maintained, and a window of +/- 7 days is allowable for CT scans and follow-up visits. During the baseline period, these windows are not applicable. Patients should be followed-up for up to 2 years.

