7.2.12 Tumor Measurement

Tumor assessments/imaging studies of the chest, abdomen, and pelvis (as clinically indicated) must be obtained at each time point listed below for all patients.

- Baseline within 28 days prior to Day 1 Cycle 1
- Every 8 weeks from the start of treatment
- Within 2 weeks of the End of Treatment Visit if the patient has discontinued treatment for reasons other than radiologic disease progression. If an End of Treatment visit is not performed, tumor measurements must be obtained at the time the patient is discontinued from treatment.
- For patients that discontinued treatment for reasons other than radiologic progression, every 8 weeks during the follow-up period until the patient develops radiologic progression or the start of new anticancer treatment.

On-site tumor assessments will be performed by the Investigator/local radiologist according to RECIST criteria (version 1.1). Results of these assessments including response for target and non-target lesions and appearance of new lesions will be the basis for the continuation or discontinuation of study medication.

If the Investigator determines that a patient develops clinical progression manifested by symptomatic deterioration but not supported by radiologic evidence of progression, the patient should stop treatment. Symptoms of clinical progression must be documented in the patient's source documents. Every effort should be made to document objective progression even after discontinuation of treatment.

If a patient is withdrawn due to radiologic disease progression, additional CT scans are not required at the End of Treatment Visit. The same method of assessment and the same technique must be used to characterize each identified and reported lesion at Baseline, throughout the study, and during the follow-up period.

All patients' files and radiological assessments must be available for source verification. Results of any unscheduled evaluations should be recorded.

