9 STATISTICS

9.1 Statistical Analysis

16-week PFS rate will be estimated by Kaplan-Meier method and expressed based on exact binomial distribution. Other survival outcomes including TTP, PFS, OS and their corresponding 95% confidence interval will be estimated using Kaplan-Meier method.

All of the reported P values will be 2-tailed, and $P < 0.05$ will be considered statistically significant. No multiplicity will be considered. The analyses will be performed using statistical software packages SPSS and R.

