Appendix 1. STUDY SCHEDULE

	Baseline Period		On Treatment Period (+/-3 days for procedures; +/-7 days for CT scans & FU)							End of Treatment Period (q8wk)		
	Baseline Day		Cycle 1				Subsequent Cycles			End of Treatment	30-day Safety FU	Survival FU
	-28 to -1	-7 to -1	1	12	15	End of recovery	1	12	15			
Procedure	x											
Sign ICF	x											
Enrolment	x											
Medical History	x											
Physical Examination		x					x			x	x	
Baseline signs and symptoms	x											
ECG	x											
Vital signs, height, body weight		x					x			x	x	
ECOG performance status	x		x				x			x	x	
Hematology		x			x		x		x	x	x	
Serum chemistry		x			x		x		x	x	x	
CA 19-9		x			x		x		x	x	x	
Urinalysis		x										
Pregnancy Test		x										
Tumor measurement	x								x	x		x
Concomitant Medications	x	➔	➔	➔	➔	➔	➔	➔	➔	➔	➔	➔
AE / SAE assessment		x	➔	➔	➔	➔	➔	➔	➔	➔	➔	➔
Survival status		x	➔	➔	➔	➔	➔	➔	➔	➔	➔	➔
Quality of life assessment		x										
Exploratory biomarker	x		x				x					
TAS-102 treatment			x (D1-5)	x (D8-12)			x (D1-5)	x (D8-12)				

Footnotes:

- (1) Sign ICF: Written informed consent should be obtained prior to the performance of any study procedure
- (2) Vital Signs: Heart rate, blood pressure, body temperature, respiratory rate; collect at the start of every cycle; collect within 24 hours prior to Day 1 study drug administration.
- (3) Blood tests within 28 days prior to study assessment include complete blood count, liver function test, renal function test, eGFR, coagulation profile & hepatitis B status.
- (4) Tumor Measurements: Obtain a contrast-enhanced computed tomography (CT) scan of the chest and abdomen (and pelvis, if clinically indicated) within 28 days prior to Day 1 of Cycle 1 and **every 8 weeks thereafter** during study treatment. If a patient discontinues treatment due to radiologic disease progression, additional tumor assessment is not required at the End of Treatment visit. For patients who discontinue treatment for reasons other than radiologic disease progression, every effort should be made to perform an end of treatment tumor assessment prior to the start of new anticancer therapy. Patients that discontinued treatment for reasons other than disease progression should continue to be followed for tumor response every 8 weeks until the patient develops radiologic disease progression (or death) or initiation of new anticancer therapy.

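### The 16-week PFS landmark is counted from informed consent but scans from first dose, so progression first seen on the week-16 scan usually counts as progression-free

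*Protocol*

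**What the plan says.** - **Endpoint clock.** Protocol 7.3.1 counts patients "alive and without progression (according to RECIST 1.1) at 16 weeks from the date of informed consent". In 7.3.2, "PFS is measured from the date of informed consent to radiographically documented progression according to RECIST 1.1 or death from any cause"; TTP has the same origin.
- **Scan clock.** Section 7.2.12 requires imaging "Every 8 weeks from the start of treatment". Section 7.1 adds that "a window of +/- 7 days is allowable for CT scans and follow-up visits".
- **Gap between the clocks.** Appendix 1 marks signing of the consent form in the Day -28 to -1 column, and its first footnote says "Written informed consent should be obtained prior to the performance of any study procedure". Consent therefore precedes first dose by 1 to 28 days.
- **Other imaging.** Section 7.2.12 also asks for a scan "Within 2 weeks of the End of Treatment Visit if the patient has discontinued treatment for reasons other than radiologic disease progression", and "Results of any unscheduled evaluations should be recorded".
- **Analysis.** Section 9.1: "16-week PFS rate will be estimated by Kaplan-Meier method and expressed based on exact binomial distribution". Section 9.3 sets a null rate of 10%, an alternative of 30%, 28 patients, and a positive conclusion if at least 6 of the first 25 evaluable patients are successes.

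Nothing in 7.3, 9.1 or 9.3 ties the week-16 scan to the 16-week landmark.

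**The concern.** Progression becomes an event only when it is documented on imaging. If the week-16 scan falls after day 112 from consent, its result can no longer make a patient a failure at day 112. A clean late scan rightly confirms success. A late scan that shows progression gives a PFS time above 16 weeks, which is also a success. Failures by day 112 then come mainly from the week-8 scan, deaths, and any end-of-treatment or unscheduled imaging. Progression between the week-8 scan and the landmark is otherwise missed.

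The error runs one way, upward relative to true 16-week status, and it feeds the trial's only decision rule. If the historical 10% reflects true 16-week status, an inactive drug is more likely than planned to be declared worthy of further study.

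**Working it through.** **1. The design as stated.** With X binomial on n = 25:
- P(X ≥ 6 | 0.10) = 0.0334
- P(X ≥ 6 | 0.30) = 0.807
- 25 / 0.90 = 27.8, rounded up to 28

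The sample size and cut-off reproduce, with one-sided error 0.033 and power 0.81.

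**2. Dates.** Let g be the days from consent to first dose (1 to 28) and o the scan deviation (-7 to +7).
- Week-8 scan, from consent: day 56 + g + o, that is day 50 to 91.
- Week-16 scan, from consent: day 112 + g + o. This is day 113 to 140 on schedule and day 106 to 147 with the window.

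The week-16 scan falls on or before day 112 only if g + o ≤ 0. That holds for 28 of the 420 (g, o) pairs and for none with g ≥ 8. This is a count of permitted combinations, not a forecast of frequency.

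**3. Illustrative size.** Assumptions not in the protocol: constant hazard with true status 10% at day 112 from consent, so S(t) = exp(-t ln10 / 112); g and o uniform. Let L be the last scheduled scan on or before day 112, d the share of events that are deaths, and f the share of the remaining missed events recorded by day 112 in some other way.

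Measured rate = 0.10 + (1 - d)(1 - f)(mean S(L) - 0.10), with mean S(L) = 0.226.

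| Scenario | d = 0 | d = 0.25 | d = 0.50 |
|---|---|---|---|
| f = 0: measured rate | 0.226 | 0.194 | 0.163 |
| f = 0: P(X ≥ 6) | 0.51 | 0.36 | 0.21 |
| f = 0.5: measured rate | 0.163 | 0.147 | 0.131 |
| f = 0.5: P(X ≥ 6) | 0.21 | 0.15 | 0.10 |
| g = 1 to 7 only, f = 0: P(X ≥ 6) | 0.58 | 0.41 | 0.24 |

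**4. Sensitivity.**
- *By gap*, scans on nominal days, d = f = 0, rate S(56 + g): g = 1 gives 0.310 and P = 0.83; g = 14 gives 0.237 and 0.56; g = 28 gives 0.178 and 0.28.
- *Slack in the rule.* P(X ≥ 6) reaches 0.05 at a rate of 0.1101. The share of otherwise missed events that must be captured is 1 - 0.0101 / 0.1259 = 0.92.
- *Shape of the curve.* The constant hazard implies a median of 112 × ln2 / ln10 = 33.7 days, or 1.1 months, below every median PFS in Tables 1 and 2 (1.6 to 4.1 months). A Weibull curve with median 1.6 months and the same 10% at day 112 (shape 1.44) gives rates of 0.293, 0.244 and 0.196, and P = 0.78, 0.60 and 0.37.

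**5. Would moving the origin be enough?** Set g = 0. Seven of the 15 window days (113 to 119) are still after day 112. A Kaplan-Meier curve read at day 112 gives rates of 0.206, 0.179 and 0.153, and P = 0.41, 0.28 and 0.17. If status is instead taken through the in-window week-16 scan with no deaths, the rate is mean S(112 + o) = 0.1004 and P = 0.034, in line with the design.

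**The case against.** **A different reading.** Section 7.3.1 defines a status, and 9.3 counts patients whose 16-week status can be assessed. One could take the week-16 scan as that assessment, so that progression on it is a failure. But 9.1 estimates the rate by Kaplan-Meier, and the PFS definition dates progression from consent. Followed literally, those two sections put the event after day 112.

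**Left to the SAP.** Rules that map scans to a landmark often sit there. Step 5 shows that, under uniform windows, most of the excess remains after the origin is moved: (0.410 - 0.033) / (0.510 - 0.033) = 0.79. With every scan on its nominal day, however, the origin accounts for all of it. The consent origin is written into the protocol's primary endpoint, and 9.2 requires an amendment to change that endpoint. The point that stands is that the fix needs both parts.

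**Appendix 1.** The table as extracted marks tumor measurement under Day 15 of subsequent cycles. Read literally, scans would fall 42 and 98 days after first dose, and half of the (g, o) pairs would put the second on or before day 112. The step 3 formula with mean S(L) = 0.197 then gives P of about 0.37, 0.25 and 0.16. The mark conflicts with 7.2.12 and the appendix's own footnote 4, and may be an extraction fault.

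**Size and direction.** Patients stop treatment on clinical progression and are to be scanned, and deaths are common in this disease, so 0.51 is at the high end for its model. The protocol gives neither the time origin nor the scan interval behind the historical 10%. If that rate carries a similar lag, the excess shrinks. Both limits stand.

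**Keeping consent.** A sentence assigning the week-16 scan to the landmark could remove most of the problem with consent kept as origin. The landmark would then be a visit up to 35 days beyond the stated 16 weeks.

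**Conclusion.** The protocol is wrong as written. For every permitted gap, the on-schedule week-16 scan falls 1 to 28 days after the landmark. Even with the full window it can fall on or before day 112 only when the gap is 7 days or less and the scan is early by at least that many days. This follows from the protocol's dates alone. The measured 16-week rate is biased upward relative to true status.

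No single figure for the size is established. Under the constant-hazard averages, the chance of passing the rule at a true 10% runs from 0.10 (half of events deaths, half of the remainder imaged early) to 0.51 (neither), against 0.033. Holding it at 0.05 would need about 92% of the events missed by scheduled scans to be recorded by day 112 in some other way. Whether this is also a bias against the 10% null depends on how the historical rate was measured, which the protocol does not state. It should be corrected because it affects the primary endpoint and the sole go/no-go rule.

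**What to change.** 1. **7.3.1, and PFS and TTP in 7.3.2:** measure from Cycle 1 Day 1. The OS origin need not change.
2. **7.3.1:** define 16-week success as alive with no RECIST 1.1 progression up to and including the scheduled week-16 scan within its ±7-day window. Progression on that scan is then a failure whatever its exact day.
3. **9.1:** make the exact binomial proportion on this definition the primary estimate. Align any Kaplan-Meier 16-week figure with it, either by assigning in-window scans to the nominal week-16 date or by reading the curve at day 119. The first route avoids counting deaths in the following week against a 16-week rate.
4. **Appendix 1:** make the tumor-measurement marks agree with 7.2.12 and footnote 4.

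The cost is a protocol amendment, which 9.2 requires for a change to the primary endpoint. No scans, visits or patients are added, and 28 patients with the 6-of-25 rule (error 0.033, power 0.81) stand. The reported 16-week rate and PFS will look somewhat less favourable.
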